5.2.3 Analysis for MRI endpoints

MRI is measured from all subjects in this study.. Records up to 28 days after the first dose can be used as baseline assessments. If there are multiple records, then the one closest to the first dosing date will be selected; if tied, then the record prior to the first dose will be defined as baseline.

At each visit where MRI data is available, the number of Gd+ lesions , the number of T1 hypointense lesions, and the number of new or newly enlarged T2 hyperintense lesions, will be summarized both as continuous variables and as categorical variables (number of lesions being 0, 1, 2, 3 and ≥ 4).

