### **13.5. Secondary Endpoints Analysis**

#### **13.5.1. Efficacy Analysis**

The proportion of subjects relapse-free at Month 12 will be estimated using Kaplan-Meier approach. This will be calculated as 1 minus the proportion of subjects with relapses at Month 12. For the Kaplan Meier approach, the time to relapse is the number of days from the date of the first dose of daclizumab to the date of first relapse, or end of study, whichever comes first. The Cox proportional hazard model will be used to estimate the hazard ratio of relapses between subject subgroups of interest.

The proportion of subjects relapse-free 12 months before and 12 months after switching to daclizumab will be compared using McNemar's Test for subjects who had relapse information available at the above time points (study completers).

The proportion of subjects experiencing relapse requiring hospitalization and/or steroid treatment at Month 12 will be estimated using the Kaplan-Meier approach. For the Kaplan-Meier approach, the time to relapse requiring hospitalization and/or steroid treatment will be the number of days from the date of the first dose of daclizumab to the date of first relapse requiring hospitalization and/or steroids treatment, or end of study, whichever comes first. A Cox proportional hazard model will be used to estimate the hazard ratio of relapses requiring hospitalization and/or steroids treatment between subject subgroups of interest.

The ARR with 95% CI at Month 12 (calculated as the total number of relapses divided by the total number of person-years in the study at the end of Month 12 for each subject) will be estimated using a negative binomial model. If the data are under-dispersed or if the negative binomial regression does not converge, a Poisson regression model with the same covariates will be used instead. Given that subjects may have more than 1 relapse in 12 months, the number of relapses will be summarized both as a continuous variable and as a categorical variable.

The number of new Gd+ enhanced and T1 hypointense lesions at Month 6 and Month 12 and the number of new or newly enlarged T2 hyperintense lesions at Month 6 and Month 12 when compared with baseline will be summarized both as continuous variables and as categorical variables. A negative binomial model adjusting for the corresponding baseline MRI lesion counts will be used to estimate the adjusted mean and lesion mean ratio between subject subgroups of interest.

CONFIDENTIAL

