1.2 Secondary Objectives and Endpoints

The secondary objectives are to evaluate the effects of daclizumab beta on the following:

- Multiple Sclerosis (MS) relapse activity including annualized relapse rate (ARR) and the proportion of subjects experiencing relapses requiring hospitalization and/or steroid treatment.
- MS-related outcomes measured using magnetic resonance imaging (MRI).
- Safety and tolerability in subjects previously treated with natalizumab.

The secondary endpoints are:

- The proportion of subjects relapse-free at Month 12.
- The proportion of subjects experiencing relapse requiring hospitalization and/or steroid treatment at Month 12.
- The ARR at Month 12.
- The number of new gadolinium enhanced (Gd+) and T1 hypointense lesions at Month 6 and Month 12 on MRI.
- The number of new or newly enlarged T2 hyperintense lesions at Month 6 and Month 12 on MRI.
- The permanent discontinuation rate of daclizumab beta at Month 12.
- The incidence of adverse events (AEs) and serious adverse events (SAEs) including clinically relevant.

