4.3 Demographics and Baseline Characteristics

Demographic data, including age (years), age category (<18, 18-19, 20-29, 30-39, 40-49, 50-55, and >55, also ≤ 35 , > 35), gender, race category, baseline height (cm) and weight (kg) will be summarized.

Baseline data are defined as data collected on the closest date prior to or on the first dosing date. Baseline disease characteristics will be summarized. These include years since disease (MS) onset, years since diagnosis, McDonald criteria, number of relapses in the past 12 months and in the past 3 years, [REDACTED], [REDACTED], baseline MRI, prior MS treatment history, medical history, tobacco use, and status of interferon binding and neutralizing antibodies. Additional variables may be included where applicable.

All demographic and baseline data will be summarized for the full analysis set.

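### The SAP 5.2.3 MRI baseline rule lets a post-dose scan displace a valid pre-dose scan, at odds with SAP 4.3, and the same section omits *new* from the Gd+ and T1 lesion counts

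*SAP*

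**What the plan says.** **Baseline.** SAP 4.3 gives the general rule: "Baseline data are defined as data collected on the closest date prior to or on the first dosing date". Its list of baseline characteristics to be summarised includes "baseline MRI, prior MS treatment history". SAP 5.2.3 gives a different rule for MRI: "Records up to 28 days after the first dose can be used as baseline assessments". Where a subject has several records, "the one closest to the first dosing date will be selected; if tied, then the record prior to the first dose" is taken as baseline. Post-dose scans are not restricted to subjects who lack a pre-dose scan.

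**Schedule.** Protocol Table 1 places enrollment on Day −31 to −1 and Month 1 within 4 days either side of its target. Footnote 2 requires the screening MRI at least 7 days before first dose and lets later scans precede their visit by up to 4 days. Month 1 is a scheduled MRI visit.

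**Lesion counts.** SAP 1.2 defines the endpoint as "The number of new gadolinium enhanced (Gd+) and T1 hypointense lesions at Month 6 and Month 12 on MRI". Protocol 13.5.1 analyses "The number of new Gd+ enhanced and T1 hypointense lesions at Month 6 and Month 12". SAP 5.2.3 instead summarises as follows: "At each visit where MRI data is available, the number of Gd+ lesions", then "the number of T1 hypointense lesions, and the number of new or newly enlarged T2 hyperintense lesions". *New* is kept for T2 and absent for Gd+ and T1.

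**The concern.** A baseline scan should describe the subject before study treatment. The nearest-scan rule in 5.2.3 can pass over a valid pre-dose scan for one taken up to four weeks into treatment, and the schedule allows this without any protocol deviation. Two programmers working from 4.3 and 5.2.3 could build different baseline MRI tables from the same data.

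The choice matters because of what such a scan shows. First dose is 28 to 31 days after the last natalizumab infusion. A scan on Day 20 to 28 therefore falls 28 + 20 = 48 to 31 + 28 = 59 days after that infusion. Protocol 5.2.1 says natalizumab becomes undetectable at 8 weeks (56 days) and that disease activity can return within 6 months of stopping. The scan belongs to the switch period under study.

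The missing *new* is a separate matter. A count of all T1 hypointense lesions includes those present before daclizumab, so it answers a different question from the secondary endpoint.

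**Working it through.** The plan gives no figure on this point, so there is none to reproduce. The check applies the 5.2.3 rule to every allowed pair of scan days.

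**Inputs.** Day 0 is first dose. Let *p* be the screening scan day and *s* the Month 1 scan day.
- *p*: Day −31 to −7 (25 days) at the widest, from Table 1 and footnote 2. Day −28 to −7 (22 days) and Day −20 to −7 are narrower cases.
- *s*: month length plus a visit deviation of −4 to +4 days (9 values). The scan is taken either at the visit or 0 to 4 days before it (5 values).
- Month length is not given; 28, 30 and 31 days are assumed. All days are assumed equally likely.

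**Rule.** Under 5.2.3 the Month 1 scan displaces the screening scan when *s* ≤ 28 and *s* < |*p*|. Under 4.3 this never happens.

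**Examples.** Screening on Day −28 with Month 1 scan on Day 24: 5.2.3 takes Day 24 and 4.3 takes Day −28. Day −24 with Day 24 is a tie, so the pre-dose scan is kept. Day −7 with Day 24: the pre-dose scan is kept.

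**Counts.** For a given *s* up to 28, the number of screening days displaced is 31 − *s* in the widest window and 28 − *s* in the narrower one.
- Widest window, 28-day month, scan at visit: *s* = 24 to 28 gives 7 + 6 + 5 + 4 + 3 = 25 of 25 × 9 = 225.
- Widest window, 28-day month, scan 0–4 days before visit: *s* = 20 to 28 arises in 1, 2, 3, 4, 5, 5, 5, 5, 5 of the 9 × 5 = 45 combinations. This gives 11 + 20 + 27 + 32 + 35 + 30 + 25 + 20 + 15 = 215 of 25 × 45 = 1125.
- For 30- and 31-day months with the early allowance, the same weights start at *s* = 22 and 23. In the Day −28 window this gives 6 + 10 + 12 + 12 + 10 + 5 = 55 and 5 + 8 + 9 + 8 + 5 = 35, each of 22 × 45 = 990.

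| Screening window | Month (days) | Scan at visit | Scan 0–4 days before visit |
|---|---|---|---|
| Day −31 to −7 | 28 | 25/225 = 11.1% | 215/1125 = 19.1% |
| | 30 | 12/225 = 5.3% | 130/1125 = 11.6% |
| | 31 | 7/225 = 3.1% | 95/1125 = 8.4% |
| Day −28 to −7 | 28 | 10/198 = 5.1% | 110/990 = 11.1% |
| | 30 | 3/198 = 1.5% | 55/990 = 5.6% |
| | 31 | 1/198 = 0.5% | 35/990 = 3.5% |
| Day −20 to −7 | any | 0% | 0% |

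The last row is zero because the earliest possible Month 1 scan is Day 20, which can at best tie.

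**Subjects.** SAP 4 reports approximately 30 enrolled. 0.5% × 30 = 0.15, 5.1% × 30 = 1.5 and 19.1% × 30 = 5.7, so about 0 to 6. Protocol 9.1 counts a subject as enrolled at consent, whereas the analysis set is dosed subjects, so the denominator may be smaller. Unscheduled scans are not counted here.

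**Lesion wording.** SAP 1.2 and Protocol 13.5.1 put *new* before the Gd+ and T1 pair, and Protocol 13.5.1 sets the counts against baseline. SAP 5.2.3 has *new* only for T2, within one sentence. SAP 4 allows endpoints to be dropped or listed after early termination but does not redefine this one. Where SAP 5.2 drops an endpoint (permanent discontinuation), it says so.

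**The case against.** The case on the other side is substantial, and most of it limits the size of the point.

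- *The baseline table may be unaffected.* The only planned baseline MRI summary is in SAP 4.3, directly after the on-or-before-first-dose definition. If 4.3 governs its own table, the pre-dose scan is used. If 5.2.3 is a deliberate override, there is no conflict, only a poor choice. This stands as far as it goes: a reader might infer that the table will certainly contain post-dose scans, and the text does not establish that. It establishes that the SAP does not say which rule applies.
- *Month 1 reporting.* A reader might infer that a scan used as baseline is lost from Month 1. SAP 5.2.3 summarises every visit with MRI data, and nothing removes the scan, so that inference is not supported.
- *T2 counts.* A reader might infer that early T2 lesions are absorbed into baseline and the Month 6 count is too low. That needs the central reader's reference scan to follow the SAP rule. Protocol 13.5.1 refers to comparison with baseline, but neither document says how the reader's reference is chosen; Protocol 11.3.3 points to a separate MRI manual for the reading center's results. No effect on T2 is shown.
- *Drug effect on the baseline scan.* Protocol 5.2.1 puts visible Gd+ reductions at 8 to 12 weeks, so daclizumab's effect by Day 28 may be small. This stands. The fault is discarding an available pre-dose scan.
- *The upper figure stacks wide assumptions.* If screening starts with the last natalizumab dose, Day −31 to −29 is reachable only by subjects dosed after Day 28. Protocol 7.2 gives one 4-day window either side for all assessments, so adding the scan allowance is only one reading. Without both, the range is 0.5–5.1%. If the screening MRI was meant to fall within the 7 days before dosing, no scheduled Month 1 scan could displace it.
- *The missing word may be shorthand.* Section 5.2.3 is headed as the analysis of the MRI endpoints, its wording resembles the assessment list in Protocol 11.2.2.4, and *new* in SAP 1.2 could be read as attaching to Gd+ alone. The natural reading covers both lesion types, and the SAP does not say that the shorter wording is shorthand.

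**Conclusion.** Both parts hold, at minor severity.

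As written, SAP 5.2.3 can replace a valid pre-dose scan with the Month 1 scan. It can therefore give a subject a different baseline from SAP 4.3, and nothing says which rule feeds the baseline MRI summary. Under the stated assumptions this affects 0% to 19.1% of subjects, with 0.5–5.1% for the narrower window and scans at the visit: about 0 to 6 of approximately 30. These figures rest on assumed uniform scan days and month length, not on data.

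The consequence is confined to the descriptive baseline MRI summary, and only if 5.2.3 governs it. Protocol 13.5.1 planned a model adjusted for baseline lesion counts, but SAP 5.2.3 carries only summaries, so the Gd+ and T1 counts as written do not use the baseline. No test and no primary result is affected. The documents give no lesion rate for this population, so no bias in lesion counts can be estimated.

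Read literally, the T1 count includes lesions present before treatment and does not estimate the stated endpoint. For Gd+ the difference is probably small, because Protocol 8.2 excludes subjects with Gd+ lesions in the 6 months before screening.

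**What to change.** In SAP 5.2.3, define MRI baseline as the last scan on or before first dose, as in SAP 4.3. Use a post-dose scan, up to Day 28, only when no pre-dose scan exists, and flag those subjects in the baseline summary.

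Summarise new Gd+ and new T1 hypointense lesions where the central reader supplies them, and name the reference scan. Otherwise label the counts as totals and state that the new-lesion endpoint is not analysed.

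The cost is SAP wording; no scans need to be re-read. The downside is a few flagged or missing baselines and possibly an explicit statement that a secondary endpoint is not analysed.

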5.3 Exploratory Analyses

Because the study is not fully enrolled due to the global withdrawal of daclizumab, the

[REDACTED]

5.3.1 Analysis for disability progression

Due to the early termination of this study,

[REDACTED]

- [REDACTED]
- [REDACTED]
- [REDACTED]
- [REDACTED]

5.3.2 Analysis for exploratory biomarkers

[REDACTED]

[REDACTED]

[REDACTED]

5.4 Safety Analysis

Safety analysis will be performed with data from the entire study period.

5.4.1 Clinical Adverse Events

Treatment-emergent adverse event (TEAE) is defined as an adverse event having onset date on or after the first dosing date and prior to the 180 days after the last dosing date, or if it was present prior to start of study treatment and subsequently worsened. If it cannot be determined whether an event is treatment emergent due to a missing or partial date, then the event will be tabulated as treatment emergent. Adverse events will be coded using the Medical Dictionary for Regulatory Activities (MedDRA). Only treatment-emergent adverse events (TEAE) will be presented in the summary tables.

In general, AE tables include the following (but not limited to):

- incidence of treatment-emergent adverse events will be summarized overall and by severity (mild, moderate and severe);
- TEAE's will also be presented by system organ class (SOC) and preferred terms (PT) and sorted by decreasing frequency of PT within SOC, if there is sufficient data. If a patient experiences an event more than once with varying severity during the study, he/she will be counted only once with the maximum severity within each SOC and PT;
- the incidence of serious adverse events (SAE) will be summarized by system organ class (SOC) and preferred terms (PT) and sorted by frequency if there is sufficient data; otherwise listings for individual patients who experienced SAEs will be generated;
- any incidence of adverse events that lead to the dose interruption, discontinuation of study drug or premature withdrawal from the study will be presented; a listing of these adverse events may also be presented;
- any deaths that occurred during the study will be listed and relevant information including timing of the death relative to study treatment, reason of death, concomitant medications, the investigator assessment of the cause of death will be provided;
- incidences of adverse events of special interest (AESI) will also be presented, if there is sufficient data; otherwise listings of AESI will be generated. These adverse event of special interest categories are defined mainly based on Standardized MedDRA Queries (SMQs), SOC's, and/or PT's. The AEs of special interest categories may include but are not limited to the following:
 - Infections, including serious infections and potential opportunistic infections
 - Cutaneous events, including serious events
 - Hepatic disorders
 - Gastrointestinal events
 - Autoimmune disorders
 - Injection site reactions
 - Depression and suicide ideation
 - Malignancies, potential and those confirmed upon medical review

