4 GENERAL CONSIDERATIONS

The SUSTAIN study was terminated early by sponsor upon the withdrawal of daclizumab from the global market after approximately 30 subjects were enrolled in study. Because the study was not fully enrolled and there was limited follow-up time, some endpoints will no longer be analyzed and some endpoints and outcomes will be summarized in listings rather than data tabulations. Missing data in this study will not be imputed.

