4.1 Treatment Period Definitions

Based on the schedule of assessment, we have the following definitions:

- **the first dosing date** is the date when the subject is first dosed;
- **the last dosing date** is the date of the last date the subject is dosed;
- **The end of study date** is the last visit date;

- **Treatment period, or, time on (study) treatment**, is defined as the time between the first dosing date and the last dosing date; it is calculated as the last dosing date minus the first dosing date + 1; also known as the time exposed to study drug;
- **Time on study, or study period**, is defined as the time between the first dosing date and the end of study date, calculated as the last visit date – the first dosing date + 1.

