4.6 General Information on Statistical Analysis

Summary statistics will be generated for all efficacy, safety, PK/PD parameters, demographic/baseline variables and other variables where applicable. For the continuous endpoints, the summary statistics will generally include number of subjects, mean, standard deviation, median, 25th and 75th percentile, minimum and maximum. For categorical endpoints, the summary statistics will generally include number of subjects in corresponding analysis population, number and the percentage of subjects in each category.

In general, all efficacy endpoint analyses where applicable will include the baseline covariates; the covariates included in the statistical models for efficacy endpoints are selected to be consistent with analysis models in other previously reported Phase 3 MS studies.

All statistical tests will be 2-sided with an overall type I error rate of 0.05; no multiple testing adjustment will be performed in this study.

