4.8 Alternative Multiple Sclerosis Medications

In this study, alternative MS medications refers to a list of medications including but not limited to methotrexate, glatimer acetate, mycophenolate mofetil, azathioprine, natalizumab, alemtuzumab, teriflunomide, mitoxantrone, fingolimod, dimethyl fumarate, rituximab, ocrelizumab, laquinimod, and interferon beta throughout this document. Patients who take alternative MS medications during the study will be listed.

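### SAP 5.4.1 gives adverse event incidence only as percentages of dosed subjects, with no exposure denominator and no split between events on daclizumab, after it, and after a switch

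*SAP*

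**What the plan says.** The incidence of AEs and SAEs is a secondary endpoint (Protocol 6.1.2, SAP 1.2). No time point is attached to it, whereas the relapse, ARR, MRI and discontinuation endpoints name Month 6, Month 12 or both.

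- **Measure.** SAP 5.4.1 plans that the "incidence of treatment-emergent adverse events will be summarized overall and by severity (mild, moderate and severe"), with further tables for SAEs and events of special interest. SAP 4.6 defines categorical summaries as the "number and the percentage of subjects in each category". The denominator is the full analysis set, that is, everyone with at least one dose (SAP 3).
- **Time covered.** SAP 5.4: "Safety analysis will be performed with data from the entire study period". In SAP 4.1 the study period "is defined as the time between the first dosing date and the end of study date". A treatment-emergent event is one "having onset date on or after the first dosing date and prior to the 180 days after the last dosing date", or one already present that worsened.
- **Setting.** SAP 2 records enrolment planned over about 12 months and a stop of drug supply linked to the withdrawal of 2 March 2018. SAP 4 records about 30 subjects and explains the reduced analyses: "Because the study was not fully enrolled and there was limited follow-up time".
- **Replacement drugs.** SAP 4.5 summarises the number and percentage of subjects who switch. SAP 4.8 adds: "Patients who take alternative MS medications during the study will be listed". Neither is linked to the AE tables.
- **Exposure.** SAP 4.2 reports median follow-up and median time on treatment; SAP 4.4 reports injections received.
- **Relapses, for contrast.** SAP 5.2.2 divides relapses by days on treatment and by days on study, and reports both.

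**The concern.** Two features of the AE tables make their percentages hard to interpret.

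First, a percentage of subjects with an event depends on how long each subject was watched. Subjects who entered at different times and lost supply at about the same calendar time will have been exposed for different lengths of time. The SAP was written with the early stop known and uses person-time for relapses, but not for safety.

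Second, the window pools three kinds of time: on daclizumab, off it but untreated, and on another MS drug. Subjects whose supply has ended can be expected to move to other treatment, and the SAP foresees this. A reader of the AE table cannot tell which events fall where. Protocol 13.5.2.3 promised AEs by relationship to study treatment. The tables named in SAP 5.4.1 mention severity only, although that list is expressly open-ended.

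After a market withdrawal, safety is the main lasting output of an abbreviated report. Its percentages may be set beside those in Protocol 5.1.4 (SAEs in 15% and cutaneous events in 37% of daclizumab subjects in a study of 96 to 144 weeks), with nothing in the tables to show how far follow-up differed.

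**Working it through.** The documents state no AE rate, AE precision or exposure distribution, so there is no planned figure to reproduce on this point. The only design figure concerns the primary endpoint (Protocol 13.1) and is sound: 1.96 × √(0.80 × 0.20 / 90) = 8.3% and 1.96 × √(0.88 × 0.12 / 90) = 6.7%, as stated.

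**Inputs.** From the documents: about 30 subjects (SAP 4); 12 months of planned treatment (SAP 2); 4 months of follow-up after stopping (Protocol 7.2); a 180-day window (SAP 5.4.1). Assumed: a constant hazard, and on-treatment time uniform over 1 to 12 months.

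**1. How follow-up time moves a crude percentage.** For a 12-month risk R, the monthly hazard is λ = −ln(1 − R)/12. With T uniform over 1 to 12 months, the expected crude percentage is

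1 − [exp(−λ) − exp(−12λ)] / (11λ).

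For R = 20%, λ = 0.018595. The fraction is (0.98158 − 0.80000)/0.20455 = 0.8877, so the crude percentage is 11.2%. Adding m months off drug at the same hazard multiplies 0.8877 by exp(−λm):

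- 4 months: 0.8877 × 0.9283 = 0.8241, giving 17.6%.
- 180 days (5.91 months): 0.8877 × 0.8959 = 0.7953, giving 20.5%.

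| 12-month risk | On treatment only | Plus 4 months | Plus 180 days |
|---|---|---|---|
| 10% | 5.5% | 8.8% | 10.3% |
| 20% | 11.2% | 17.6% | 20.5% |
| 40% | 23.5% | 35.5% | 40.5% |

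Relative to the 12-month risk, the first column is 41% to 45% low, the second 11% to 12% low, and the third not low at all. The first column depends heavily on the assumed exposure: the shortfall is 21% to 24% for 6 to 12 months and 66% to 70% for 1 to 6 months.

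**2. How much time at risk is off drug.** Exposure uniform over 1 to 12 months averages 6.5 months, so 30 × 6.5/12 = 16.25 person-years on drug. Four months each afterwards adds 30 × 4/12 = 10 person-years. The off-drug share is 10/26.25 = 38%. It would be 10/40 = 25% if all had 12 months on drug, and 10/17.5 = 57% if all had 3.

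**3. What pooling does to a rate.** Assume an on-drug rate of 0.50 first events per person-year and an off-drug rate k times that. The pooled rate is (0.50 × 16.25 + k × 0.50 × 10)/26.25:

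- k = 0: 0.31
- k = 0.5: 0.41
- k = 1: 0.50
- k = 2: 0.69

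Pooling can therefore push the figure either way, and changes nothing if the two rates are equal.

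**4. Window against follow-up.** Four months is about 120 days, so roughly the last 60 days of the 180-day window lie beyond the remote safety visit and may be only partly observed.

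**The case against.** The strongest case against is that a reader might infer more than the documents support.

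- **That the tables understate the 12-month risk by 41% to 45%.** This counts on-treatment time only. The planned table also counts post-drug events, and at equal hazard the shortfall falls to 11% to 12% with 4 months and vanishes with 180 days. Short exposure and pooling pull against each other and cannot both apply at full size.
- **That the trial was meant to show a 12-month AE risk.** The AE endpoint names no time point.
- **That exposure ran from one dose to 12.** No distribution is given. Unequal exposure is a fair inference from staggered entry and a common stop; its range is not.
- **That use of replacement drugs is merely listed.** SAP 4.5 also summarises it, and for deaths SAP 5.4.1 asks for timing relative to treatment and concomitant medications.
- **That the post-dose window is an error.** Looking for delayed outcomes is a stated purpose of the safety follow-up (Protocol 4.2, 11.2.2.3). Protocol 5.1.4 reports that drug concentration and the NK-cell marker returned to pre-treatment values during a 24-week washout (168 days), close to 180 days.

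The comparison figures of 15% and 37% are themselves percentages of subjects, and the SAP plans no formal comparison. The report is descriptive and single-arm, with about 30 subjects, and SAE and special-interest tables fall back to listings when data are sparse.

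All of this stands, and it limits the point to interpretability. It does not supply the missing denominator or the missing split, and medians in the disposition table cannot be turned into event rates.

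**Conclusion.** The point holds as a cheap improvement. SAP 5.4.1 plans percentages of dosed subjects without person-time, and pools events on daclizumab with events up to 180 days after it, including any after a switch. Those percentages will be a correct description of what was seen. They cannot be read as daclizumab's risk over a defined period.

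It would be tempting to conclude that the risk is misstated, or misstated downwards. The documents do not show that: with no exposure times, event counts or switch dates, neither the size nor the direction of any distortion can be known. The figures of about 11%, 18% and 20% to 21% for a 20% 12-month risk show only how strongly the table depends on follow-up time. They rest on an assumed constant hazard, an assumed uniform exposure and an assumed equal off-drug hazard.

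**What to change.** Keep the crude percentages and the 180-day window, and add to SAP 5.4.1:

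1. Person-years, and first-event rates per 100 person-years with exact Poisson 95% confidence intervals, for any TEAE, for SAEs and for special-interest groups with sufficient data. Report them for the treatment period and the study period, following SAP 4.1 and 5.2.2.
2. A tabulation or flag by onset: during treatment; after the last dose but before any alternative MS drug; after starting one. Protocol 7.2 already collects MS treatment and concomitant medications after stopping.
3. A stated and justified on-treatment cut, so that delayed drug effects are not relabelled as off-drug. The SAP 4.1 treatment period ends on the last dosing date, so a subject with a single dose would contribute one day; using it unchanged needs a reason.
4. A reconciliation of the 180-day window with the 4-month safety follow-up, stating how time after the last contact is handled.

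The cost is SAP wording and some programming, with no new data collection. The rates assume a roughly constant hazard, which is why the percentages stay alongside. Intervals will be wide: with the assumed 16.25 person-years on drug and no events, the upper exact limit is −ln(0.025)/16.25 = 3.69/16.25, or about 23 per 100 person-years.
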